**Table 4: Standardized criteria for GQi severity score assessment**

Candidate Parameter		Method of measurement and scores	
Symptoms of PQD	Ia: TCM Inquiry (Cold frequency)	No cold in the past 2 months	0
		Once in the past 2 months	1
		Twice in the past 2 months	2
		3 times or more in the past 2 months	3
	Ib1: TCM Inquiry (Spontaneous sweating)	No spontaneous sweating, sweat only with intense physical activities	0
		Sweat with routine physical activities	1
		Sweat heavily with routine physical activities	2
		Sweat with slight physical activities like walking	3
		Sweat spontaneously	4
	Ib2: TCM Inquiry (Aversion to wind & cold)	No aversion to wind or cold	0
		Aversion to wind	1
		Aversion to cold, but relieved by adding light clothing	2
Aversion to both cold (but relieved by light clothing) and wind, or susceptible to cold when exposed to wind or cold		3	
Aversion to cold (only relieved by thick clothing that covers whole body); or very easily catch a cold when exposed to wind or cold		4	
Symptoms of Systemic Qi Deficiency	IIa: TCM Inquiry (Limb weakness)	1-5 scale, with 5 indicating the most symptomatic	
	IIb: TCM Inquiry (Lack of energy)		
	IIc: TCM Inquiry (Low spirit)		
	IId: TCM Inquiry (Unwilling to talk)		
Symptoms of Lung Qi Deficiency	IIIa: TCM Inquiry (Shortness of Breath)	1-5 scale, with 5 indicating the most symptomatic	
	IIIb: TCM Inquiry (Cough)		
	IIIc: TCM Inquiry (Thin sputum)		
	IIId: TCM Inquiry (Timidity)		
Symptoms of Spleen Qi Deficiency	Iva: TCM Inquiry (Poor appetite)	1-5 scale, with 5 indicating the most symptomatic	
	IVb: TCM Inquiry (Loose stools)		
	IVc: TCM Inquiry (Abdominal discomfort feeling after eating)		
Symptoms of Heart Qi Deficiency	Va: TCM Inquiry (Palpitations)	1-5 scale, with 5 indicating the most symptomatic	
	Vb: TCM Inquiry (Depressed)		
Symptoms of Kidney Qi Deficiency	VIa: TCM Inquiry (Urination)	1-5 scale, with 5 indicating the most symptomatic	
	VIb: TCM Inquiry (Soreness of lower back)	1-5 scale, with 5 indicating the most symptomatic	
	VIc: TCM Inquiry (Cold limbs especially legs)	1-5 scale, with 5 indicating the most symptomatic	
Sign of GQD	Part I: TCM Auscultation (Low voice & apathy)	The participant's voice is loud & clear at a distance of 2m from the investigator	0
		The participant can be heard & understood at 2m from the investigator, but the voice is recognizably weak.	1
		The participant's voice is clearly low at 2m from the investigator & needs much attention to understand.	2
		The participant can be heard from 2m but need repeated clarification.	3
		The participant cannot be heard with a clear understanding at a distance of 2m.	4
	Part II: TCM Inspection (Tongue)	The tongue looks light red with thin white coating and is of proper size.	0
		The tongue looks pale in color with white coating; however, the tongue is of proper size & has no tooth mark on the sides.	1
		The tongue looks pale with white coating. This size is slightly larger than normal. Tooth-marks are visible but are limited to part(s) of the tip and sides of the tongue.	2
		The tongue looks pale with white coating. This size is significantly larger than normal. Tooth-marks are visible along the full length of the tip and sides of the tongue.	3
	Part III: TCM Palpation (Overall Pulse)	Normal pulse	0
		Deficient Pulse is detectable but not apparent	1
		Apparent Deficient Pulse	2
	Part IV: TCM Palpation (Cun Puls)	Normal pulse	0
The pulse shows characteristics of Floating or Deficient Pulse, but not both.		1	
Floating pulse is present, Deficient Pulse is detectable but not apparent.		2	
Floating pulse is present, Deficient Pulse is apparent.		3	

Overall pulse indicates the overall impression of pulse at the three locations: Cun, Guan, & Chi.

# Appendix 1

## Subject Record at Screening

### Participant questionnaire – General Information

1. Date of birth:
2. Gender:
3. Ethnicity:
4. Telephone number:
5. Email:
6. What was the last time you were vaccinated?
  - a. If yes, what vaccine?
7. Taking medications ? If yes:
  - a. What is the name of the medication?
  - b. When did you begin taking the medication?
  - c. What is the dosage?
  - d. How often do you take the medication?
8. Are you a female who is pregnant or is attempting to become pregnant, or is lactating?
9. Have you consumed other dietary supplements within 30 days? If yes:
  - a. What is the name of the supplement?
  - b. When did you begin taking the supplement?
  - c. What is the dosage?
  - d. How often do you take the supplement?
10. Have you participated as a subject in any other clinical study within 30 days?
11. Do you have any gastrointestinal conditions that may affect consumption of the treatment or placebo tablets?
12. Do you smoke? If yes, how often and how much do you smoke?
13. Do you have a history of alcohol consumption within the previous 2 years? If so, how many drinks do you have each week?

14. Are you fully able and willing to keep scheduled appointments (once every 2 weeks for the full 12 week duration)?
15. Do you have allergies to mushrooms or other fungi , or yeast products?
16. Do you have had a medical surgery in the past 4 weeks or have scheduled a surgery during the study period?
17. Do you have a history of substance abuse within the previous 2 years?
18. Please check any acute or chronic illnesses you currently have:
  - Diabetes
  - Acute infection, contagious diseases
  - Chronic bronchitis
  - Cardiopulmonary failure
  - Cancer
  - Immune dysfunction or disorder
  - Significant constipation or diarrhea
  - Alzheimer's and other neurodegenerative diseases
  - depression or anxiety disorders
  - Any other significant illnesses
19. If you have a cold during time of the trial, are you willing follow the investigating doctors' prescription and refrain from other medications?

## Subject Record at Screening

### Participant questionnaire – PQi and GQi Evaluation Questionnaire

#### Endpoint Part I

1. Did you catch any cold\* (\*as defined by TCM) in the past three months?
2. If no, please proceed to Part II
3. If yes:
  - a. how many times, and how long did it last?
    - i. Once duration:
    - ii. Twice duration of cold #1:  
duration of cold #2:
    - iii. 3 times or more duration of cold #1:  
duration of cold #2:  
duration of cold #3:  
duration of other colds:
  - b. how many days since you last experienced symptoms of a cold\*? If you currently have an ongoing cold, write “ongoing”.

Please rate each question on 1-10 scale

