## **5. Study Population**

### **5.1 Inclusion Criteria**

1. Male or females aged 18 to 65 years (inclusive) without regard to race or ethnic background
2. Provide a signed Informed Consent prior to entry in the study.

3. Willing to follow all study instructions and consume the assigned investigational product for 12 weeks.
4. Not currently taking a  $\beta$ -glucan containing supplement or any other supplement that might interfere with the study design.
5. Ability to swallow tablets and pills.
6. Exhibit a PQD severity score  $> 1.8$  (calculated by Table 1 & Table 2)

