## 5.5 Strategies for Recruitment and Retention

Subjects will be recruited through referral from other TCM practitioners and advertisement on social media. Individuals who were believed to have PQD by referring practitioners or by themselves will be encouraged to apply. Potential subjects recruited through TCM practitioners will not be referred without prior consent. All potential subjects will report to the TCM clinic for a screening visit (Visit 1, **Section 1.2**) prior to enrollment into the study. At screening, all potential subjects will be provided with an Information and Consent Form (ICF) and provided with sufficient time to read the ICF. Thereafter, a TCM practitioner will review the ICF with each potential subject and will address any questions the potential subject may have concerning the ICF and/or the clinical trial. The potential subject will also be provided with the option of taking the ICF home for review prior to making his or her decision to enroll or not enroll in the study. If potential subjects refuse consent, they will be asked to leave the clinic and will not be enrolled in the study. If they provide consent, the potential subject will sign the consent form, receive a duplicate for their own records, and will be considered as consented subjects.

Once consent has been obtained, a TCM practitioner will initiate the screening process (Appendix 1) that includes collection of information concerning anthropometric, general health status as well as PQi status. If the potential applicants exhibit a PQD severity score  $\leq 1.8$  (see Table 1 & Table 2), which, according to our preliminary study, represents less responsiveness to the treatment, they will be excluded from the trial, whereas the applicants with a score  $>1.8$  will begin the enrollment process.

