**Table 2: Standardized criteria for PQi severity score assessment**

Candidate Parameter		Method of measurement and scores	
Cold Frequency	TCM Inquiry (Cold frequency)	No cold in the past 2 months	0
		Once in the past 2 months	1
		Twice in the past 2 months	2
		3 times or more in the past 2 months	3
Symptoms of PQD	TCM Inquiry (Spontaneous sweating)	No spontaneous sweating, sweat only with intense physical activities	0
		Sweat with routine physical activities	1
		Sweat heavily with routine physical activities	2
		Sweat with slight physical activities like walking	3
		Sweat spontaneously	4
	TCM Inquiry (Aversion to wind & cold)	No aversion to wind or cold	0
		Aversion to wind	1
		Aversion to cold, but relieved by adding light clothing	2
		Aversion to both cold (but relieved by light clothing) and wind, or susceptible to cold when exposed to wind or cold	3
		Aversion to cold (only relieved by thick clothing that covers whole body); or very easily catch a cold when exposed to wind or cold	4
Sign of PQD	TCM Auscultation (Low voice & apathy)	The participant's voice is loud & clear at a distance of 2m from the investigator	0
		The participant can be heard & understood at 2m from the investigator, but the voice is recognizably weak.	1
		The participant's voice is clearly low at 2m from the investigator & needs much attention to understand.	2
		The participant can be heard from 2m but need repeated clarification.	3
		The participant cannot be heard with a clear understanding at a distance of 2m.	4
	TCM Inspection (Tongue)	The tongue looks light red with thin white coating and is of proper size.	0
		The tongue looks pale in color with white coating; however, the tongue is of proper size & has no tooth mark on the sides.	1
		The tongue looks pale with white coating. This size is slightly larger than normal. Tooth-marks are visible but are limited to part(s) of the tip and sides of the tongue.	2
		The tongue looks pale with white coating. This size is significantly larger than normal. Tooth-marks are visible along the full length of the tip and sides of the tongue.	3
	TCM Palpation (Overall Pulse  )	Normal pulse	0
		Deficient Pulse is detectable but not apparent	1
		Apparent Deficient Pulse	2
	TCM Palpation (Cun Puls  )	Normal pulse	0
		The pulse shows characteristics of Floating or Deficient Pulse, but not both.	1
		Floating pulse is present, Deficient Pulse is detectable but not apparent.	2

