### Subject Record at Follow-up

#### Participant questionnaire – PQi and GQi Evaluation Questionnaire

##### Part I

Do you have a history of **catching** a cold\* (\*, defined by TCM) in the past year? If no, please proceed to Part II of this section; if yes, please fill out the following blanks.

1. How many times did you **catch** a cold\* in the **past year**?

i. Once

duration:

ii. Twice

duration of cold #1:

duration of cold #2:

iii. 3 times or more

duration of cold #1:

duration of cold #2:

duration of cold #3:

duration of other colds:

iv. During the above colds\*, did you experience any of the following symptoms:

- Sneezing
- Coughing
- Sweating
- Nasal discharge or congestion
- High fever (body temperature  $> 39.1^{\circ}\text{C}$ )
- Itching or painful throat
- Headache
- Aversion to wind and cold
- General pain and malaise

2. How many times did you **catch** a cold\* **last winter (2017 – 2018)**?

i. Once

duration:

ii. Twice

duration of cold #1:

duration of cold #2:

iii. 3 times or more

duration of cold #1:

duration of cold #2:

duration of cold #3:

duration of other colds:

iv. During the above colds\*, did you experience any of the following symptoms:

- Sneezing
- Coughing
- Sweating
- Nasal discharge or congestion
- High fever (body temperature > 39.1C)
- Itching or painful throat
- Headache
- Aversion to wind and cold
- General pain and malaise

3. How many times did you **catch** a cold\* in the **last two months**?

i. Once

duration:

ii. Twice

duration of cold #1:

duration of cold #2:

iii. 3 times or more

duration of cold #1:

duration of cold #2:

duration of cold #3:

duration of other colds:

iv. During the above colds\*, did you experience any of the following symptoms:

- Sneezing
- Coughing
- Sweating
- Nasal discharge or congestion
- Itching or painful throat
- Headache
- Aversion to wind and cold
- General pain and malaise
- High fever (body temperature > 39.1C)

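### The screening form counts colds over three months while the score behind the >1.8 entry cut counts two, so the entry score can be too high and, for same-day enrollees, so can the baseline

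*Combined protocol and SAP*

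**What the plan says.** All sections cited are in the combined protocol and SAP unless stated otherwise.

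- **Entry rule.** Section 5.1, item 6 requires a PQD severity score above 1.8, "calculated by Table 1 & Table 2". Section 5.5 repeats the cut and explains that lower scorers responded less in the preliminary study.
- **Scoring window.** Table 2 codes colds 0 to 3, from "No cold in the past 2 months" through "Once in the past 2 months" and twice, up to three or more in the same period. Table 1 gives the item a weight of 25%. Attachments I and II of the separate protocol document also use two months.
- **Screening form.** Under section 5.5, "a TCM practitioner will initiate the screening process (Appendix 1") and this is where PQi status is collected. The only cold-count question in Appendix 1 (Endpoint Part I) covers colds "in the past three months". It asks how long each cold lasted and how many days have passed since the last symptoms, but not when earlier colds occurred.
- **Follow-up form.** Item 3 of Appendix 4, Part I, asks about the "last two months". The same part opens with a question about colds "in the past year? If no, please proceed to Part II of this section", and items 1 and 2 cover the past year and the previous winter.
- **Visit 1.** Section 5.5 says that anyone enrolled on a later day (within 14 days) is re-assessed with Appendix 4, and that Visit 1 status replaces screening status in the analysis. Anyone enrolled on the screening day counts as having completed both visits; no Appendix 4 re-assessment is stated for them.

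**The concern.** The form that feeds the entry decision looks back 50% further than the score it feeds, and no section gives a conversion. A three-month count cannot be smaller than the two-month count it contains, so if it is entered as the Table 2 code, any error raises the score.

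Two things are at stake. First, the cut exists to keep out people expected to respond less, and a longer window can admit some of them. Second, if a three-month count stands as baseline and later visits use two months, the cold item will tend to fall on both arms for a reason unrelated to treatment. Change from baseline in this score is a primary outcome (sections 9.1 and 9.4.2).

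**Working it through.** **Inputs.** Table 1 weights: cold 0.25, sweating 0.167, aversion 0.167, tongue 0.083, voice 0.067, overall pulse 0.10, cun pulse 0.167. Table 2 maximum codes, in the same order: 3, 4, 4, 3, 4, 2, 3. Cut: above 1.8. The documents give no cold rate, so rates of 0.25, 0.5 and 0.75 per month are assumed.

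**The plan's own figure.** The plan gives no figure for the effect of the recall window. The nearest is the 1–5 range stated under Table 1. The printed codes do not reproduce it: the minimum is 0 and the maximum is 0.75 + 0.668 + 0.668 + 0.249 + 0.268 + 0.20 + 0.501 = 3.304. Some rescaling is therefore unstated, and the size of the shift is given both ways below.

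**Shift per extra cold.**
- Printed codes: 0.25 × 1 = 0.25, at most 0.25 × 3 = 0.75.
- Cold item rescaled to 1–5: 0.25 × 4/3 = 0.333, at most 1.0.

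**Who crosses the cut.** On printed codes, one extra cold moves a score over 1.8 if the two-month score is above 1.80 − 0.25 = 1.55 and at most 1.80. Such scores are attainable. Take cold 1, sweating 2, aversion 2, tongue 2, voice 1, overall pulse 1, cun pulse 2: 0.25 + 0.334 + 0.334 + 0.166 + 0.067 + 0.10 + 0.334 = 1.585, not eligible. One more cold, in the third month back, gives 1.835, eligible.

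**Average size.** Let colds follow a Poisson distribution with constant rate r per month, with the code capped at 3.
- Mean rise = 0.25 × (E[min(N₃, 3)] − E[min(N₂, 3)]), where N₃ has mean 3r and N₂ has mean 2r.
- Share whose code rises = P(N₂ ≤ 2) × (1 − e^(−r)).

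| r per month | E, 2 months | E, 3 months | Mean rise (printed codes) | Any cold in the extra month | Code actually rises |
|---|---|---|---|---|---|
| 0.25 | 0.498 | 0.742 | 0.061 | 22% | 22% |
| 0.5 | 0.977 | 1.410 | 0.108 | 39% | 36% |
| 0.75 | 1.410 | 1.943 | 0.133 | 53% | 43% |

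The last two columns differ because a person already at three colds in two months cannot score higher. These are averages over candidates, not over those enrolled, and they assume that the three-month count is entered directly.

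**Can the form repair itself?** With one cold, days since last symptoms can show that it ended more than two months ago. With two or more, only the latest is placed in time; the durations of the others do not date them.

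**The case against.** The strongest reply has four parts.

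1. **Practitioners may apply the two-month categories anyway.** The entry score is defined by Table 2, whose categories state the window, and licensed practitioners do the scoring. This stands as far as it goes: a reader might infer that entry scores are in fact inflated and that people have qualified wrongly, but the documents do not say that the three-month count is entered as the code. They support only that it can be. They also give staff no reliable way to recover a two-month count from Appendix 1 after more than one cold.
2. **Visit 1 replaces screening.** For later-day enrollees this largely removes the baseline problem. It removes the entry problem only in part, because the re-check asks whether the person still exhibits PQD and does not restate the 1.8 cut.
3. **Appendix 4 is probably completed at Visit 1 by everyone.** Section 9.4.2 needs a baseline GQi score, and Appendix 1 as printed lacks items such as cough, sputum, appetite, stools, palpitations and urination, which appear in Appendix 4. This is a reasonable inference, and it weakens the baseline concern for same-day enrollees. It remains an inference: section 5.5 does not state it.
4. **Both arms are treated alike.** This stands. A reader might infer that the treatment comparison is biased. Randomisation spreads any window artefact over both arms, so the between-arm contrast is not biased on average.

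Nor is the follow-up form purely a two-month form. It also asks about the past year and the previous winter, so the item that feeds Table 2 needs naming there too.

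**Conclusion.** The concern holds as an inconsistency that bears on a decision threshold. The screening form and the score defining the >1.8 cut use different look-back periods, the form cannot reliably bridge them, and any resulting error is upward. One extra cold is worth 0.25 points on the printed codes (about 0.33 if the cold item is rescaled to 1–5), enough to move anyone above 1.55 and at most 1.80 over the cut. The averages, 0.06 to 0.13 points with 22% to 43% of candidates affected, depend on the assumed rates, a constant Poisson process and direct use of the three-month count. How many candidates lie in the 1.55–1.80 band cannot be estimated from the documents.

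The consequences are weaker enrichment and, mainly for same-day enrollees, a possibly raised baseline with an artificial fall within both arms. It would be too strong to take the share with any cold in the extra month (39% or 53% at the higher rates) as the share whose score rises, because the cap reduces it.

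**What to change.** - Reword the Appendix 1 cold question to cover the past two months, matching Table 2 and Appendix 4 item 3.
- State that only this two-month count feeds the Table 2 cold code, and that the past-year and previous-winter items in Appendix 4 do not.
- Take the cold item for both eligibility and baseline from Appendix 4 item 3 at Visit 1 for everyone, including same-day enrollees and anyone already screened on the three-month question. Say whether the Visit 1 re-check applies the >1.8 cut.

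The cost is a small wording change, a completed Appendix 4 for same-day enrollees, and slightly more screen failures among people whose deciding cold fell in the third month back. The sample size is unaffected. Appendix 1 also asks for 1–10 ratings, which do not match the Table 2 codes; changing the window does not resolve that, and the conversion should be stated at the same time.

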#### Endpoint Part II

1. Do you have spontaneous perspiration ?
2. Does the perspiration worsen with activities?
3. Aversion to wind or chills

Score

Score

#### Endpoint Part III

1. Do you often feel shortness of breath?
2. Do you often feel unwillingness to talk?

Score

#### Endpoint Part IV

1. Do you often feel limb weakness?
2. Do you often feel lack of energy?
3. Do you often feel low spirit?

Endpoint Part V

Score

(Score each on a 1-10 scale)

1. weak or powerless pulse
2. cun-pulse superficial or weak
3. corpulent tongue or with white fur
4. low voice

Endpoint Part VI:

**iPQ Scoring Summary Table**

TCM Endpoint	Total Score	Average Score
Participant Questionnaire - Endpoint Part I		
Participant Questionnaire - Endpoint Part II		
Physical Examination – Endpoint Part II		
Overall Score		

**Traditional Diagnosis of IPQ and IQ**

	PQD	GQD
No Insufficiency		
Mild Insufficiency		
Moderate Insufficiency		
Severe Insufficiency		

Part VII: Base on what Exclusion Criteria is this subject excluded?

## Appendix 2

### Subject Record at Screening

#### PHYSICAL EXAMINATION

NOT DONE

SITE	NORMAL	ABNORMAL	NOT DONE	DESCRIBE ABNORMALITIES
General Appearance				
Head				
Eyes				
Nose				
Mouth				
Throat				
Neck				
Thyroid				
Lungs				
Heart				
Breasts				
Abdomen				
Musculoskeletal				

Investigator Signature \_\_\_\_\_

## Appendix 3

### Subject Record at Follow-up

#### Participant questionnaire – General information

1. Date of birth:
2. Gender:
3. Ethnicity:
4. Telephone number:
5. Email:
6. Height:
7. Weight:
8. Blood Pressure:
9. Heart Rate:
10. Respiration Rate:
11. Have you had a flu shot since October 1 of 2018?
12. How many days have elapsed since you last experienced symptoms of a cold\*? If you currently have an ongoing cold, write “ongoing”.
13. What was the last time you were vaccinated with something other than the flu vaccine?
  - a. If yes, what was vaccine?
14. Taking medications ?      If yes:
  - b. What is the name of the medication?
  - c. When did you begin taking the medication?
  - d. What is the dosage?
  - e. How often do you take the medication?
15. Are you a female who is pregnant or is attempting to become pregnant, or is lactating?
16. Have you consumed other dietary supplements within 30 days? If yes:
  - f. What is the name of the supplement?
  - g. When did you begin taking the supplement?

- h. What is the dosage?
- i. How often do you take the supplement?

17. Have you participated as a subject in any other clinical study within 30 days?
18. Do you have any gastrointestinal conditions that may affect consumption of the treatment or placebo tablets?
19. Do you smoke? If yes, how often and how much do you smoke?
20. Do you consume alcohol? If so, in the past 2 months, how many drinks did you consume each week on average?
21. Are you fully able and willing to keep scheduled appointments (once every 2 weeks for the full 12 week duration)?
22. Do you have allergies to mushrooms, fungi or yeast products?
23. Have had a medical surgery in the past 4 weeks and/or do you have a medical surgery scheduled during the study period?
24. Do you have a history of substance abuse within the previous 2 years?
25. Have you suffered from allergic rhinitis, or pollinosis (hay fever), or asthma in the past year?
26. Did you eat any mushroom or oatmeal in the past two months?

If yes, please state the approximate average quantity in a week (grams/week)?

27. Please check any acute or chronic illnesses you currently have:

Diabetes

Acute infection, contagious diseases

Chronic bronchitis

Cardiopulmonary failure

Cancer

Immune dysfunction or disorder

Significant constipation or diarrhea

Alzheimer's and other neurodegenerative diseases

Depression or anxiety disorders

Any other significant illnesses

28. If you have a cold during time of the trial, are you willing to inform and follow the study doctor's instructions?

## Appendix 4

